8.1 Sample Size Considerations

The number of Participants to be enrolled in this 6-month extension study depends upon the number of subjects who complete the Day 180 Visit in Study VMDN-003-2 and provide written informed consent for this extension protocol (prior to or during their Day 180 Visit in the VMDN-003-2 study).

8.2 Randomization

There will be no randomization of Participants in this VMDN-003-2b extension study. All Participants who are entered into the VMDN-003-2b extension study will continue to be followed from the VMDN-003-02 study in a blinded fashion.

9.0 Population Sets

9.1 Intent-to-Treat (ITT) Population

This subset includes all enrolled Participants in this study who start this extension study at the Day 180 Visit (Study VMDN-003-2). Participants in the ITT population will be analyzed according to original treatment assignment in Study VMDN-003-2, regardless of actual treatment received. The primary analyses of the primary and secondary efficacy endpoints will be based on this ITT population.

9.2 Safety Population

The safety population will contain all enrolled Participants. Participants in the Safety population will be analyzed according to actual treatment received in Study VMDN-003-2, regardless of original treatment assigned.

9.3 Modified Intent-to-Treat (mITT) Population

The modified ITT (mITT) population includes all participants that meet the following:

- Underwent (any) injections in Study VMDN-003-2
- Correctly completed the BPI-DPN eDiary at Baseline and the 12-month follow-up (with at least 5 of 7 days of BPI-DPN eDiary collected prior to Day 365 Visit) in Study VMDN-003-2b. Participants will be grouped based on the randomly assigned treatments, not the actual treatment received. The mITT population will be used in the sensitivity analyses for the primary and secondary efficacy endpoints.

9.4 Per Protocol (PP) Populations

The Per Protocol population is a subset of mITT. It includes all mITT participants who meet all of the following criteria for Study VMDN-003-2 and Study VMDN-003-2b:

- The participant meets major protocol eligibility criteria determined by Clinical Data Review Committee (CDRC) prior to database lock and breaking the randomization codes.
- The participant received all 32 injections from each visit (Day 0, Day 14, Day 90 and Day 104) in Study VMDN-003-2, based on the randomized treatments and had a Day 365 Visit, including a 7-day ADPS (with at least 5 of 7 days of BPI-DPN eDiary collected prior to Day 365 Visit).

The CDRC, which is blinded to the treatment information of each participant, may determine additional criteria, if any, before unblinding the randomization code.

The PP population will be used in the sensitivity analyses for the primary and secondary efficacy endpoints.

10.0 Conventions and Derivations

Data screening will be conducted in a blinded fashion periodically during the conduct of the study. The objective of the data screening is to assess the quantity, quality, and statistical characteristics of the data relative to the requirements of the planned analyses. The designated Contract Research Organization (CRO) will be responsible for data cleaning and dictionary coding of AEs, medical history, and medications. Any questionable values or situations will be reported to the CDRC for final review and confirmation.

10.1 Study Day

Because VMDN-003-2b is a 6-month extension study following Study VMDN-003-2, Study Day 0 is defined as the date of first dose in the main study VMDN-003-2. Study Day 180 is defined as the completion of the Day 180 Visit of Study VMDN-003-2 and enrollment into extension study VMDN-003-2b. Subsequent visits in extension study will be counted from Study Day 180.

10.2 Baseline Definition

Unless specified otherwise, the baseline value for each variable is the value recorded at the last visit on or before start of dosing in Study VMDN-003-2.

For the pain scores from the BPI-DPN eDiary, the baseline value is the Average Daily Pain Score prior to the Day 0 visit from the main study.

Note that, for eligibility, the mean of Average Daily Pain Scores of the BPI-DPN eDiary should be ≥ 4 during the 7 days prior to Day 0. For the Average Daily Pain Score calculation, at least five (5) days need to have the available scores.

10.3 Visit Windows

Data at each scheduled follow-up visit will be analyzed according to the nominal visit identified on the data record.

In case of multiple different visits with the same nominal visit designation, the visit with the visit date closest to the target days of each protocol-specified visit schedule will be used for the efficacy analyses. For visits with the same distance to the target days, the later nominal visit record will be used. Data from all visits will be provided in the data listings.

If a subject fails to complete a study visit but provides necessary eDiary data during the time period expected for that visit (i.e. based on study day relative to the date of the first dose in VMDN-003-2), those eDiary data will be used to derive applicable endpoints. Day 270 endpoint would be derived by the eDiaries recorded 7 days up to 270 days from the date of first dose in VMDN-003-2. Similarly, Day 365 endpoint would be derived by the eDiaries recorded 7 days up to 365 days from the date of first dose in VMDN-003-2. Otherwise, if subject completes study visit, then date of visit will be used to derive applicable endpoints.

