1.3. Schedule of Activities (SoA)

		Follow-	up Visits	End of Study/ET
Study Days ^a :		Day 270	Day 300	Day 365/ET
	Visit Window (days):	± 7	± 7	± 7
	d Consent (obtained prior to or during the Participant's Day 180 Study VMDN-003-2)			
1	Vital Signs, Weight	X	X	X
2	Complete Physical Examination	X	X	X
3	Retinal Fundoscopy	X		X
4	12-Lead Electrocardiogram	X		X
5	Serum Chemistry, Hematology, Lipid Profile	X		X
6	Urine Pregnancy Test			X
7	Urine Drug Analysis	X	X	X
8	HbA1c Levels			X
9	Concomitant Medications and Procedures	X	X	X
10	Accurate Pain Reporting (APR), Placebo Response Reduction (PRR)	X	X	X
11	Full Brief Pain Inventory-Diabetic Peripheral Neuropathy (BPI-DPN)	X		X
12	Partial BPI-DPN (ePRO)	•		
13	Quality of Life (SF-36, EQ-5D)	X		X
14	Patient Global Impression of Change (PGIC)	X		X
	Treatment-emergent Adverse Events (TEAEs)	4		
15	Treatment-emergent Serious Adverse Events (TESAEs)	4		
	Adverse Events of Special Interest (AESIs)	4		
16	Michigan Neuropathy Screening Instrument (MNSI)	X		X
17	Bedside Sensory Testing (BST)	X		X

FOOTNOTES FOR SCHEDULE OF ACTIVITIES

*Schedule of Activities includes activities during Screening and all Study Visits. Additional data from daily ePRO entries will be transferred directly into a study database.

Abbreviations: AESI = adverse event of special interest; APR = Accurate Pain Reporting; BMI = Body Mass Index; BPI = Brief Pain Inventory; BST = Bedside Sensory Testing; D = Day; DPN = diabetic peripheral neuropathy; ePRO = electronic diary; ET = Early Termination; EQ-5D = EuroQol Health Utilities Index; HbA1c = hemoglobin A1c; MNSI = Michigan Neuropathy Screening Instrument (MNSI); PGIC = Patient Global Impression of Change; PRR = Placebo Response Reduction; SF-36 = 36-Item Short Form Health Survey; TEAE = treatment-emergent adverse event; TESAE = treatment-emergent serious adverse event

- Study days for this extension protocol are based on the time (in days) from Day 0 in Study VMDN-003-2.
- 1. Vital Signs and Weight: Vital signs and weight will be measured on Days 270, 300, and 365/ET. After the Participant has rested in the seated position for 5 minutes, vital signs will be collected, including temperature, sitting blood pressure, heart rate, respiratory rate, and oxygen saturation on room air. The method of

Version 1.0 14 Final: 11 Feb 2021

temperature measurement should be according to the Site's policy and should be consistently applied.

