- 7. Urine Drug Analysis includes amphetamines (methamphetamine), barbiturates, benzodiazepines, buprenorphine, cannabinoid (THC), cocaine, oxycodone, methadone, opiates, phencyclidine (PCP), tricyclics (TCA), and ethyl alcohol. Cannabinoid detection is not an exclusion criterion but may be used in exploratory analyses. The urine drug analyses will be conducted on Days 270, 300, and 365/ET. Drug analyses will be performed by the central laboratory.
- **8. HbA1c** levels will be measured on Day 365/ET.
- 9. Concomitant Medications and Procedures: All medications or vaccines, including over-the-counter or prescription medicines, vitamins, herbal supplements, and procedures that the Participant receives will be recorded on Days 270, 300, and 365/ET. For each medication, treatment, or procedure, the following information will be collected: Medication trade or generic name or type of procedure, indication, start date, stop date or ongoing, dose, units, frequency, and route.
- Accurate Pain Reporting (APR): The Accurate Pain Reporting training will be conducted on Days 270, 300, and 365/ET.
 - **Placebo Response Reduction (PRR):** The Placebo Response Reduction training will be conducted on Days 270, 300, and 365/ET.
- 11. Brief Pain Inventory (BPI-DPN) Full Questionnaire will be administered through the ePRO daily starting at 7 days prior to Day 270 and Day 365/ET. The mean of the Average Daily Pain Scores (ADPSs, used for the primary endpoint) is the mean from a minimum of 5 ADPSs recorded in the 7 days prior to the Days 270 and 365/ET Visits. If the ePRO contains fewer than 5 daily entries over the 7 days prior to the Day 270 and Day 365/ET Visits, the visit must be rescheduled (up to 3 days later) so that the Participant can record 5 daily entries over the 7 days.
- **12. Brief Pain Inventory (BPI) Partial Questionnaire** (questions 3, 5, and 9a from the full questionnaire) will be completed on the ePRO every day that the full BPI is *not* conducted from the Day 180 Visit (VMDN-003-2, Initial Visit for this extension study) to the Day 365/ET Visit.

Version 1.0 15 Final: 11 Feb 2021

- 13. Quality of Life Questionnaires (SF-36, EQ-5D) will be administered on Day 270 and Day 365/ET. The study coordinator will check the questionnaires for completeness. Any omissions or ambiguous answers will be clarified by the Participant prior to leaving the clinic.
- 14. Patient Global Impression of Change (PGIC) will be administered on Days 270 and 365/ET.

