8.2. Efficacy Assessments and Procedures

8.2.1. Brief Pain Inventory for Diabetic Painful Neuropathy

The Brief Pain Inventory for Diabetic Painful Neuropathy (BPI-DPN) assessment tool (Section 10.5, Appendix 5) will be administered through use of an eDiary. The Investigator should ensure that the Participant is provided with instructions and is trained to use the eDiary and to complete the assessment tool properly before data collection begins. The BPI-DPN will be conducted using the Full BPI-DPN questionnaire and the Partial BPI-DPN questionnaire

Scores obtained from the Full BPI-DPN during the 7 days prior to the Day 270 and Day 365/ET Visits will be used to determine ADPSs. The ADPS is the mean of at least 5 daily pain scores recorded in the eDiary. If the eDiary contains fewer than 5 daily entries over the 7 days prior to the Day 270 or the Day 365/ET Visits, the Visit must be rescheduled so that the Participant can record 5 daily entries over the 7 days prior to the rescheduled Visit.

Participants will use the eDiary to rate their Average Daily Pain and Worst Daily Pain included in the Brief BPI-DPN on a daily basis from the Day 180 Visit (Study VMDN-003-2) to the Day 365/ET Visit of this extension study to allow an assessment of the level and duration of pain relief in the active treatment group versus Placebo.

Version 1.0 37 Final: 11 Feb 2021

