10.6.1 Missing Pain Scores for the Average Scores from BPI-DPN

The means of the Average Daily Pain Scores (Question 5 from the BPI-DPN) for a visit will be considered as missing if fewer than 5 of 7 days of BPI-DPN eDiary entries are provided. Any missing mean pain score of ADPS will be imputed using the methods described below.

Multiple Imputation (MI) method:

- Step 1: Intermittent missing values will first be imputed by treatment group using the Markov Chain Monte Carlo (MCMC) method, resulting in data with a monotone pattern.
- Step 2: Multiple imputation by treatment group using linear mixed model regression with factors of baseline pain score, baseline HbA1c, gender, and age at informed consent (Study VMDN-003-2) will be applied to the data obtained from the MCMC step. The imputed score will be rounded to the first decimal point.

The entire procedure will be repeated 10 times, and 10 complete datasets will be used for the analysis.

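### SAP 10.3 picks between same-label visits by distance to target alone, so if a failed Day 270 or Day 365 attempt stays on record, a pain score rescued by rescheduling can be discarded and imputed

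*SAP*

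**What the plan says.** **Protocol.** Footnote 11 of the Schedule of Activities (section 1.3) says that, with fewer than 5 entries in the 7 days before the Day 270 or Day 365/ET visit, "the visit must be rescheduled (up to 3 days later) so that the Participant can record 5 daily entries over the 7 days". Section 8.2.1 repeats the duty without a day limit: "the Visit must be rescheduled so that the Participant can record 5 daily entries over the 7 days prior to the rescheduled Visit". The visit window is 7 days either side of target.

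**SAP 10.3.** The selection rule opens with a condition, "In case of multiple different visits with the same nominal visit designation", and then says that "the visit with the visit date closest to the target days of each protocol-specified visit schedule will be used for the efficacy analyses". Ties are settled by date: "For visits with the same distance to the target days, the later nominal visit record will be used". The next paragraph gives a participant who misses a visit a score from the diary week up to Day 270 or Day 365, counted from first dose. It ends: "Otherwise, if subject completes study visit, then date of visit will be used to derive applicable endpoints".

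**SAP 10.6.1.** A visit's mean pain score "will be considered as missing if fewer than 5 of 7 days of BPI-DPN eDiary entries are provided", and a missing mean goes to multiple imputation.

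**Where the score is used.** Day 365 change in mean ADPS is the primary endpoint (Protocol 9.3.1). Day 270 enters the primary repeated-measures model (SAP 12.5.1) and is a time point for worst pain and 50% response (Protocol 9.3.2). Having 5 of 7 diary days before the Day 365 visit is also a condition for mITT (SAP 9.3), PP (SAP 9.4) and study completion (SAP 12.1).

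**The concern.** The protocol's rescheduling rule exists to turn an unusable diary week into a usable one. The SAP's selection rule does not ask which of two same-label visits has a usable week. A repeat visit always comes later than the first attempt. So if the first attempt was on or after target, the repeat is further away and loses. The analysis then takes the attempt that triggered the rescheduling, finds fewer than 5 entries, and imputes.

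At stake are observed pain scores in the participants whom the protocol rule was written to rescue. Replacing them with imputed values costs precision and makes the result lean more on the missing-data model. If mITT, PP and completion are judged on the selected record, the same participants also drop out of those groups, so the mITT and PP sensitivity analyses would not reveal the problem.

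A secondary point lies in the same section. Someone who misses the visit can receive an observed score from the calendar week. Someone who attends late with fewer than 5 entries before the visit date cannot, even if the calendar week is complete.

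**Working it through.** The documents give no figure on this point to reproduce. The check enumerates the SAP 10.3 rule.

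**Inputs**
- First attempt at target + d days, d = −7 to +7: 15 possible days (Schedule of Activities window).
- Repeat at target + d + k, k = 1 to 3 (footnote 11).
- Target day counted from Day 0 of VMDN-003-2, as in the Schedule of Activities. SAP 10.1 counts extension visits from Study Day 180, so the SAP does not fully fix the target.
- Both attempts recorded under the same nominal visit. This is an assumption that the documents do not settle.

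**Rule.** The failed attempt is selected if |d| < |d + k|. Ties go to the later visit, the repeat.

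| Delay k | Failed attempt selected when | All 15 days | Repeat kept within +7 |
|---|---|---|---|
| 1 | d ≥ 0 | 8/15 (53%) | 7/14 |
| 2 | d ≥ 0 (d = −1 is a tie) | 8/15 (53%) | 6/13 |
| 3 | d ≥ −1 | 9/15 (60%) | 6/12 |
| Total | | 25/45 (56%) | 19/39 (49%) |

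A first attempt 2 or more days early never loses the rescued score when k is at most 3.

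**Dependence on visit timing.** The fractions above are shares of participants only if all days are equally likely. The documents give no distribution of visit days. Under an assumed discretised normal on −7 to +7 with SD 1 to 4 days, the share in which the failed attempt is selected, across k = 1 to 3, is:

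| Centre of first-visit days | Share |
|---|---|
| 3 days early | 0–40% |
| 1 day early | 30–70% |
| On target | 55–94% |
| 1 day late | 64–100% |
| 3 days late | 79–100% |

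**Example.** A participant attends on Day 365 with entries on Days 358, 359, 363 and 364: 4 of 7. The visit is rescheduled to Day 368 and entries are made on Days 365, 366 and 367. The week of Days 361–367 now has entries on 363 to 367: 5 of 7, a valid mean. The distances to target are 0 and 3, so SAP 10.3 selects Day 365, and SAP 10.6.1 makes the score missing and imputes it.

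**Secondary point.** A participant attends on Day 370 with 4 of the 7 preceding days entered. SAP 10.3 ties the score to the visit date, so it is missing even if the week up to Day 365 is complete. Had the participant not attended, that same week would have supplied an observed score.

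**The case against.** The strongest reply is that a rescheduled visit is one visit moved to a later date: one record and one date. Protocol 8.2.1 ties the diary week to the rescheduled visit, and SAP 10.3 uses the date of the completed visit. On that reading the selection rule never applies and nothing is lost. The reading is natural and may match practice, but neither document states it. A shortfall may be found only once the participant has attended: Protocol 6.2.1 has the eDiary returned at each visit, and the Day 270 and Day 365 visits also carry laboratory tests, examinations and questionnaires. SAP 10.3 itself expects several visits under one label, and its completed-visit sentence does not say which date applies when there are two.

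A reader might infer that rescued scores are usually discarded. The documents do not support that. The share is about half if all visit days are equally likely, and runs from 0% to 100% across the timings tried. A reader might also infer that Day 270 scores are primary-endpoint scores. They are not: only Day 365 is primary.

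Two further replies carry some weight. SAP 10.0 sends questionable values to the blinded data review committee, which makes a silent discard less certain, although it is not a derivation rule. And mITT and PP refer to the Day 365 visit, not to the record selected under 10.3, so loss from those populations is possible rather than established.

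The secondary point is narrow. For a visit on target the two weeks essentially coincide, and the daily diary stops at the Day 365 visit, so at the primary time point it mainly concerns late attended visits. Extending the calendar week would also draw on the partial questionnaire, whereas the protocol defines these endpoints from the full BPI-DPN.

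**Conclusion.** The concern holds conditionally. If a failed attempt and its repeat are both recorded under the same nominal visit, SAP 10.3 and 10.6.1 together discard a valid observed mean whenever the first attempt was on or after target, or 1 day early with a 3-day delay. That defeats the protocol's rescheduling rule.

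The number of participants affected cannot be derived: the documents give no rescheduling rate, no visit-day distribution and no statement of how a failed attempt is recorded. The effect on the treatment estimate is therefore unquantified. The gap deserves closing because a prespecified derivation of the primary endpoint should not depend on how a site labels a repeated visit.

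The unequal treatment of missed and late-attended visits is real but secondary.

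**What to change.** **Main change, SAP 10.3.** For endpoints derived from diary pain scores, when several records share a nominal visit, first keep those with at least 5 of 7 diary days before the visit date, then take the one closest to target, with ties as now. Use the same selected week for mITT, PP and completion status. Leave the existing rule for other assessments. Under this wording the failed attempt is selected in none of the successfully rescued cases.

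**Clarifications.** State whether a failed attempt is kept as a visit record or replaced by the rescheduled one, and state one origin for the target day. The 3-day limit in footnote 11 and the unlimited wording of Protocol 8.2.1 should be reconciled.

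**Optional.** Where an attended visit has no qualifying record, the sponsor may extend the calendar-week derivation already allowed for missed visits. The SAP must then reconcile use of questions 5 and 3 from the partial questionnaire with the protocol's definition of the endpoints from the full BPI-DPN.

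**Cost.** The main change is a sentence or two and a small edit to the derivation program, made before database lock and unblinding. It needs no new data and no site work. The optional part costs more, because of the endpoint definition.

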10.4 Unmasking of Randomization Codes

Following database lock of this extension study, the randomization code will be unmasked to the project team for all subjects in the extension study and concurrently for Study VMDN-003-2. During the study, the randomization code will be unmasked to the Data Safety Monitoring Board (DSMB; Section 7.5) members and the CRO that will prepare the unmasking summary tables for the DSMB meetings. However, to prevent bias, the unmasking detailed data summaries will not be shared with the sponsor management team, the CDRC, or the team that is monitoring the clinical data collection. The participant and study personnel, including core lab, principal investigator, co-investigators, study coordinators, study monitors and study director will remain blinded to individual data and group results until all data has been entered into the database and the database is locked.

10.5 Data Safety Monitoring Board

An independent DSMB will periodically review a limited set of unblinded tables and/or listings, including all reported AEs. The objectives of the DSMB meetings are to review the safety outcomes of the study and provide guidance to the study sponsor regarding the safety of the Engensis. The data analyses for the DSMB meetings will be directly provided to the DSMB members and no data will be released to the study sponsor and blinded designees. There will be no adjustment for multiple testing due to the DSMB data review. The DSMB may be asked to review and provide guidance regarding protocol deviations that may affect the determination of the PP populations. Further details of DSMB responsibilities are included in the DSMB Charter.

10.6 Handling of Missing and Incomplete Data

Participants may have missing specific data points for a variety of reasons. In general, data may be missing due to a participant's early withdrawal from study, a missed visit, or a clinical parameter not measured at a particular point in time. The general procedures outlined below describe how missing data will be addressed in the analyses.

